6.2 Secondary Outcomes

- 6.2.1 Tumor positivity as based on standard clinical laboratory techniques and signal detection of oxy- and deoxy-hemoglobin using MSOT localization
- 6.2.2 Tumor volumes as estimated by MSOT and by standard clinical laboratory techniques
- 6.2.3 Identification of tumor and/or lymph nodes based upon either Isosulfan Blue or IC Green dye

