24	Once the surgeon has the probe in place, the MSOT operator will press the foot pedal to activate the laser radiation for imaging. The MSOT operator will communicate with the surgeon as an image is acquired and coordinate the timing of the laser activation for additional scans. Release of the foot pedal will immediately shut down the laser system and stop the imaging procedure.
25	
The MSOT operator will record Scan comments on the screen to be saved for each image acquired in the image sequence.
 
NOTE: Total number of images acquired in the image sequence will be recorded on the Imaging Case Report Form (Appendix A).

26	
A yellow indicator in the signaling device on top of the system and in the front panel shows that laser light is emitted through the aperture of the handheld probe. Keep the aperture of the probe on the region of interest or towards the floor. NEVER direct the aperture of the probe towards eyes while this indicator is on. Once the foot pedal is released laser emission is stopped and the laser emission indicator will turn off.
	
27	The patient will undergo surgery for resection of the identified volume of tissue according to standard care.	
28	After tumor or lymph node removal and incision has been closed, the area of interest will be reimaged by MSOT to obtain post-surgery images in the operating room by repeating steps 16 through 23.	
29	An estimate of the percent amount of tumor remaining will be estimated by algorithms within in the MSOT computer programming for investigational use only.	
30	The resected tumor will be taken to Pathology for volume assessment and pathological identification per medically established diagnostic standard care.	
31	Data from the MSOT imaging is for research purposes only and not for treatment, and digital images will be kept on the MSOT computer, which will be stored in a secured room accessible only to study personnel.	
32	Key parameters will be recorded on (Appendix A and B).	

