10.2 Analysis of Secondary Objective

10.2.1 There are three secondary outcomes of interest, two of these will be based upon a positivity (yes/no) (secondary outcomes 1 and 3) and one of these will assess on a continuous scale tumor size/ volume (secondary outcome 2). In each of these analyses, we will compare the information gathered from the MSOT approach (size, positivity tumor (yes/no), positivity of dye (yes/no)) for each patient and then compare these measures to those that are available from information gathered in the standard of care approach (i.e., from pathology reports after resection).

For continuous outcomes we will examine three characteristics based on comparing the MSOT and standard of care (“gold standard”) assessments. These include: 1) the mean difference in the measure (i.e., tumor volume or size), 2) the correlation between the measures taken using MSOT or standard of care; and 3) the comparison of variability of the measures from the two approaches (MSOT and standard of care). For the first approach we will calculate a paired t-test, for the second we will estimate a Pearson correlation and for the third we will perform an F-test to compare the equality of variances. With the expanded sample size of 50 patients we can detect a difference in values of volume (or size) equal to 0.4 standard deviations or less of the measure of difference in tumor volumes (or size) with 80% power using a paired t-test with $\alpha=0.05$ (2-sided). In addition, there is 80% power to detect a correlation of 0.38 (or larger) with an $\alpha=0.05$ (2-sided). Finally, there is 80% power to detect a ratio of 2.24 (or larger) when comparing variances between the two groups (note: this ratio corresponds to a ratio of 1.5 on the standard deviation scale).

If the study is terminated early with 45 patients scanned, we can still detect a difference in values of volume (or size) equal to 0.43 standard deviations or less of the measure of difference in tumor volumes (or size) with 80% power using a paired t-test with

alpha=0.05 (2-sided). In addition, there is 80% power to detect a correlation of 0.40 (or larger) with an alpha=0.05 (2-sided). Additionally, there is 80% power to detect a ratio of 2.35 (or larger) when comparing variances between the two groups (note: this ratio corresponds to a ratio of 1.53 on the standard deviation scale)

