For binary outcomes (positivity and presence of dye), we will estimate the MSOT approach and the corresponding 95% Clopper-Pearson exact binomial confidence interval. Accuracy is defined as the number of patients where the MSOT and standard of care approach are in agreement (i.e., both are positive or both are negative). In addition, we can examine other characteristics of the two approaches including sensitivity, specificity, positive predictive value and negative predictive values.

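### Protocol 10.2.1 tests the variances of paired MSOT and pathology volumes with an independent-groups F-test and plans no individual-level agreement measure; the SAP gives volume no endpoint or analysis

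*Protocol*

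**What the plan says.** Protocol 6.2.2 lists as a secondary outcome "Tumor volumes as estimated by MSOT and by standard clinical laboratory techniques". Table 2, step 30 (Protocol 7.1) provides the reference value: "The resected tumor will be taken to Pathology for volume assessment".

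Protocol 10.2.1 takes the MSOT measures "for each patient and then compare these measures to those that are available from information gathered in the standard of care approach", so each patient contributes a pair. Three analyses of the continuous measure follow:

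- Mean difference: "For the first approach we will calculate a paired t-test".
- Association: a Pearson correlation.
- Variability: "for the third we will perform an F-test to compare the equality of variances".

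Power for the third is given at two sample sizes: "there is 80% power to detect a ratio of 2.24 (or larger) when comparing variances between the two groups" (50 patients) and "there is 80% power to detect a ratio of 2.35 (or larger) when comparing variances between the two groups" (45 patients).

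Agreement is defined in the same section for the binary outcomes only: "Accuracy is defined as the number of patients where the MSOT and standard of care approach are in agreement".

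The SAP keeps tumour volume as objective 1.b.iii. Its secondary endpoints (2.b) are positivity and dye identification. Its secondary analyses (7.c) cover positivity and oxy-/deoxygenation levels. Both lists run i to ii without a gap.

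**The concern.** There are three problems.

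1. **Test and design do not match.** The mean is tested as paired data, but the variances are tested as if they came from two separate groups. The closer MSOT tracks pathology, the further the F-test falls below its nominal 5% level, and the less able it is to show a moderate difference in variability.
2. **Individual differences are not reported.** The t-test addresses average bias, the correlation addresses association, and the variance test addresses spread. None says how far an MSOT value may lie from the pathology value in one patient, which is what a reader comparing a new method with a reference wants to know.
3. **The documents do not match.** A statistician working from the SAP would produce no volume result; one working from the protocol would run three tests. That leaves room to decide after the data are seen.

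**Working it through.** **Inputs.** From Protocol 10.2.1: n = 50 or 45; 80% power; ratios 2.24 and 2.35; detectable correlation 0.38 at n=50; two-sided alpha 0.05 (stated for the t-test and the correlation, and taken as the same for the variance ratio because it reproduces the figures). Assumed: the correlation rho between the two volume measures, at 0, 0.38, 0.6 and 0.8. The documents give no planning value for it; 0.38 appears only as a detectable effect.

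**1. The protocol's own figures.** For two independent normal samples with n−1 degrees of freedom each and true variance ratio R, power = P(F > F0.975/R) + P(F < F0.025/R).

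- n=50, R=2.24: F0.975(49,49) = 1.762; power 79.8%. The exact 80% ratio is 2.245.
- n=45, R=2.35: F0.975(44,44) = 1.820; power 80.0%. The exact 80% ratio is 2.350.

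Both figures reproduce.

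**2. The same F-test on correlated pairs.** Given the scaled sum of squares v of one measure, the scaled sum of squares of the other is (1−rho²) times a noncentral chi-square with n−1 degrees of freedom and noncentrality rho²v/(1−rho²). Averaging over v ~ chi-square(n−1) gives the true rejection rate.

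**3. The paired test.** Pitman-Morgan tests the correlation between within-patient sums and differences. Its true value is (R−1)/√[(R+1)² − 4·rho²·R]. Power comes from the noncentral t, averaged over chi-square(n−1).

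Normal data, n=50:

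| rho | F-test size | Power at R=1.5, F-test | Power at R=1.5, Pitman-Morgan | F-test power at R=2.24 |
|---|---|---|---|---|
| 0 | 5% | 29% | 29% | 80% |
| 0.38 | 3.5% | 27% | 33% | 82% |
| 0.6 | 1.5% | 24% | 41.5% | 85% |
| 0.8 | 0.16% | 18% | 64% | 92% |

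Pitman-Morgan keeps 5% size throughout. Its ratios for 80% power at rho 0 / 0.38 / 0.6 / 0.8 are:

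- 50 pairs: 2.245 / 2.119 / 1.922 / 1.638
- 45 pairs: 2.351 / 2.212 / 1.995 / 1.686

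**4. What a detectable correlation says about agreement.** With no bias and equal SDs, the SD of the differences is √[2(1−r)] SD of the measure. At r = 0.38 this is √1.24 = 1.114. The 95% limits of agreement are ±1.96 × 1.114 = ±2.18 SD, and the median absolute difference is 0.6745 × 1.114 = 0.75 SD. At r = 0.8 the limits are ±1.24 SD.

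**5. Sensitivity to skew.** The documents give no distribution. Assuming log-normal values with equal variances, n=50 and rho (on the log scale) 0.8, simulated false rejection on raw values, F-test against Pitman-Morgan, is:

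- log-SD 0.2: about 0.5% against 8%
- log-SD 0.5: about 7% against 25%
- log-SD 1: about 37% against 55%

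So the paired test on raw skewed values can do worse than the test it replaces.

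**The case against.** The strongest reply is that no stated power figure is wrong. That stands. The ratios 2.24 and 2.35 are also the zero-correlation case of Pitman-Morgan, and F-test power at 2.24 rises with rho. A reader might infer that the 80% claim is inflated, or that the F-test produces excess false positives. For positively correlated normal data the reverse is true: the test is conservative, and the loss is confined to ratios below the planned one.

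It can also be said that the harm depends on an assumed correlation. This stands too. At 0.38 the loss at ratio 1.5 is 27% against 33%; the gap of 18% against 64% needs rho 0.8 and a ratio that the protocol does not target.

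A reader might take ±2.18 SD to mean that MSOT and pathology typically differ by two SDs. It is the 95% limit; the median difference is 0.75 SD, and only about 7% of patients would differ by more than 2 SD.

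Limits of agreement could be called a reporting preference, since mean, correlation and variances are components of agreement. That is partly fair: the SD of the differences is already needed for the paired t-test. But nothing commits the sponsor to reporting it as a range for individual patients.

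Finally, a reader might conclude that the SAP has withdrawn volume. It has not. It is silent on endpoint and analysis while keeping the objective, and Protocol 10.2.1 still specifies the tests. The defect is a gap to be reconciled.

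**Conclusion.** The point holds in three limited parts.

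- **SAP gap.** Volume is an objective without an endpoint or analysis in the SAP, while the protocol has both. This needs no assumption.
- **Variance test.** The F-test does not fit paired data. At n=50 its size falls from 5% to between 3.5% and 0.2% for rho between 0.38 and 0.8, with the power loss at moderate ratios shown above. This rests on bivariate normality and an assumed rho. The stated 80%-power ratios are correct and are not overstated under those conditions.
- **Agreement.** No volume analysis describes individual differences. A correlation at the protocol's detectable value is compatible with wide limits.

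The sponsor should correct this, but it concerns a secondary outcome in what the SAP calls primarily a safety study. The primary safety analysis is unaffected.

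**What to change.** (a) **SAP 2.b and 7.c.** Add the volume endpoint of Protocol 6.2.2 and an analysis matching 10.2.1, or withdraw volume in both documents. State whether the measure is a volume or a linear size, and which MSOT scan is compared with pathology.

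(b) **Protocol 10.2.1.** Replace the F-test by the Pitman-Morgan test, pre-specified on log-transformed values. Do not make it the main test on raw values. State a rule for zero or undetected values: for example, report their number, leave them out of the log analysis, and repeat it with half the smallest measured value. Restate the 80%-power ratio, on the analysis scale, as the range over assumed rho in step 3 of the working: from 2.245 down to 1.638 for 50 complete pairs, and from 2.351 down to 1.686 for 45. Report the number of complete pairs, since Appendix A allows a lymph node as the target and SAP 8 rules out imputation.

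(c) **Agreement.** Keep the paired t-test and Pearson correlation, and add Bland-Altman bias and 95% limits of agreement with confidence intervals on the same scale. Expected half-widths at n=50, in SDs of the differences, are t/√n = 0.28 for the bias and t·√[1/n + 1.96²/(2(n−1))] = 0.49 for each limit.

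**Cost.** Wording in two documents and slightly more analysis, with no extra patients; a pathology volume is already planned. The sponsor should check that the case report forms have a field for it. The detectable ratio will depend on an assumed correlation, and the log scale needs the rule for zeros.

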3.1 Primary Objective(s)

- 3.1.1 To collect safety data on patients in whom MSOT was used to image tumor or lymph nodes
- 3.1.2 To evaluate skin temperature pre and post imaging (pre- and post-surgery) as part of the safety evaluation of MSOT

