Appendix A – Imaging and Tissue Data Collection Form

Study Number: OU-SCC-MSOT PID: 0 1 - _____

Investigator: [name] Surgery Date: ____/____/____

1) Tumor or Lymph Node Assessments:

a) Target tissue

Tumor

Lymph Node

b) Standard of care method of imaging

MRI _____ tumor amount

PET _____ tumor amount

CT _____ tumor amount

Other: _____ tumor amount

c) Did patient receive neoadjuvant therapy?

Yes

No

d) MSOT Image acquired?

Yes

No

e) Was an indicator dye used during surgery?

Yes

[figure not shown]
No

f) If an indicator dye used during surgery, please indicate which dye.

Isosulfan Blue IC Green

2) Location of Imaging

a) Please circle the location of the imaging (below) and provide further description as necessary

[https://anatomyclass123.com /](https://anatomyclass123.com/)

b) Erythema post-MSOT Imaging (RTOG)

i. Time after imaging: (hr: min) _____

ii. Grade (RTOG)

- 0 No erythema present
- 1 Follicular, faint or dull erythema, epilation, dry desquamation, decreased sweating
- 2 Tender or bright erythema, patchy moist desquamation, moderate edema
- 3 Confluent, moist desquamations other than skin folds, pitting, edema
- 4 Ulceration, hemorrhage, necrosis

3) Clinical Pathology Assessment

a) Date or diagnosis (month / year):

b) Positive tumor tissue:

Yes No
 c) For Pancreatic melanoma breast HNSCC ovarian (check one) indicate stage at diagnosis (**TNM classification**):

Tx T0 Tis T1 T2 T3 T4
 Nx N0 N1 N2 N3
 Mx M0 M1

d) Tumor subtype (if applicable) _____

4) Skin temperatures

Pre-Surgery MSOT imaging			
Pre-imaging Skin Temperature (°C)		Time	
Post-imaging Skin Temperature (°C)		Time	

Post-Surgery MSOT imaging			
Pre-imaging Skin Temperature (°C)		Time	
Post-imaging Skin Temperature (°C)		Time	

5) Patient Monitoring (*)please note that patients must be monitored daily for adverse events until discharge). Please answer yes or no if Erythema at grade III or higher or change in skin pigmentation occurs.**

Yes No

_____ Post surgery	_____ 8 day
_____ 1 day	_____ 9 day
_____ 2 day	_____ 10 day
_____ 3 day	_____ 11 day
_____ 4 day	_____ 12 day
_____ 5 day	_____ 13 day
_____ 6 day	_____ 14 day
_____ 7 day	_____ 15 day

Discharge date: _____

6) Adverse event. Please answer yes or no if Erythema at grade III or higher or change in skin pigmentation occurs.

Yes No

If yes, please fill out details below:

_____ Erythema _____ Time _____ Date

_____ Changes in skin pigmentation _____ Date

7) MSOT Scan Times:

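### Protocol 10.2 reverses the direction of its paired-t power statements: 0.4 and 0.43 SD are about the smallest tumor-volume differences with 80% power, not the largest

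*Protocol*

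**What the plan says.** Protocol 10.2 plans three comparisons of MSOT tumor volume (or size) with the standard-of-care measure: a paired t-test, a Pearson correlation and an F-test of variances. For the t-test at 50 patients it claims that "we can detect a difference in values of volume (or size) equal to 0.4 standard deviations or less", on the scale "of the measure of difference in tumor volumes (or size"), and "with 80% power using a paired t-test with" two-sided alpha 0.05. If the study ends at 45 patients, "we can still detect a difference in values of volume (or size) equal to 0.43 standard deviations or less", with the same power and alpha.

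The same section words the other two claims the opposite way. The correlations (0.38 at 50 patients, 0.40 at 45) and the variance ratios (2.24 and 2.35) are each followed by *or larger*.

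On who supplies a volume:
- Protocol 3.1.1 gives the safety objective as "To collect safety data on patients in whom MSOT was used to image tumor or lymph nodes".
- Appendix A item 1a records "Target tissue" as tumor or lymph node.
- The volume objective (3.2.3) and outcome (6.2.2) concern tumor only.
- SAP section 8 rules out imputation.

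**The concern.** Power rises with the size of the true difference. A test with 80% power at 0.4 SD has less than 80% at every smaller value, so a claim of 80% power for 0.4 SD or less is false everywhere below 0.4.

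What is at stake is how a null result is read. Taken literally, the sentence offers 80% assurance against arbitrarily small differences between MSOT and the reference. A non-significant paired test could then be cited as evidence of close agreement that the sample cannot give.

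A lesser point is that the power figures use the total number of patients scanned as the number of tumor-volume pairs. Any scanned patient without both volumes lowers that number.

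**Working it through.** **Inputs (Protocol 10.2).** Pairs n = 50 or 45; effect d = mean difference divided by the SD of the differences, 0.40 or 0.43; two-sided alpha 0.05; stated power 80%.

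**Formula.** For a paired t-test with n pairs, df = n − 1, noncentrality δ = d√n, and c = the 0.975 quantile of t on df. Power = P(T > c) + P(T < −c), where T is noncentral t with df and δ.

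**Step 1: reproduce the plan's figures.**
- n = 50, d = 0.40: δ = 0.40 × √50 = 2.828, c = 2.010, power 79.2%.
- n = 45, d = 0.43: δ = 0.43 × √45 = 2.885, c = 2.015, power 80.5%.

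Both agree with the stated 80%. One-sided alpha would give 87.4% and 88.4%, so the two-sided test is the one used.

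**Step 2: power below the stated difference.**

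| True difference (SD) | Power, 50 pairs | Power, 45 pairs |
|---|---|---|
| 0.43 | 84.6% | 80.5% |
| 0.40 | 79.2% | 74.7% |
| 0.30 | 54.8% | 50.3% |
| 0.20 | 28.4% | 25.9% |

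With 50 pairs, a true difference of 0.2 SD would be missed about 72% of the time (100 − 28.4 = 71.6). Power of 80% would need 90 pairs at 0.3 SD and 199 pairs at 0.2 SD.

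**Step 3: exact detectable difference.** Solving power = 80% for d gives 0.404 SD at 50 pairs and 0.427 SD at 45.

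**Step 4 (secondary): fewer pairs.** The documents give no expected number of evaluable pairs, so 40, 30 and 20 are assumptions chosen to show a range. The detectable correlation is tanh[(1.960 + 0.842)/√(n − 3)], by Fisher z. The detectable variance ratio R solves P(F > c/R) + P(F < 1/(cR)) = 0.80, where F has (n − 1, n − 1) df and c is its 0.975 quantile. At 50 and 45 pairs this gives 2.24 and 2.35, the plan's own values.

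| Pairs | Power at 0.4 SD | Detectable difference (SD) | Detectable correlation | Detectable variance ratio |
|---|---|---|---|---|
| 50 | 79% | 0.40 | 0.39 | 2.24 |
| 45 | 75% | 0.43 | 0.41 | 2.35 |
| 40 | 69% | 0.45 | 0.43 | 2.48 |
| 30 | 56% | 0.53 | 0.49 | 2.88 |
| 20 | 40% | 0.66 | 0.59 | 3.74 |

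The Fisher approximation gives 0.387 and 0.407 where the plan has 0.38 and 0.40. That is about 78% power at the plan's values, close enough that nothing turns on it.

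**The case against.** **The wording can be read charitably.** *Or less* might describe the threshold, meaning that the detectable difference is at most 0.4 or 0.43 SD. At 45 pairs that is literally true (0.427), and at 50 it misses by only 0.004 (0.404). But the correlation and variance-ratio claims in the same section say *or larger* at both sample sizes, so the natural reading is a range of true effects, and that range runs the wrong way.

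**No number changes.** This stands. Both figures reproduce, and no sample size, test or decision depends on the phrase. Volume is a secondary outcome, and section 10.3 justifies the sample size by the adverse-event confidence interval. The protocol also sets no agreement or success rule on the paired test, so misreading a null result is a risk, not a planned step.

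**The pair count may be met in full.** A reader might infer from the tumor-or-node target that node-target patients give no volume pair and that the design cannot supply 50. The documents do not support this:
- Inclusion criterion 4.1.1 requires a solid tumor scheduled for removal.
- Table 2 step 30 sends the resected tumor to Pathology for volume assessment, so the reference half of the pair is planned for everyone.
- Appendix A item 1a does not say that only one target may be ticked, or that a node-target patient's tumor goes unmeasured by MSOT.
- Section 10.2 already restates its figures for 45 patients, the one reduced total the protocol plans.

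What remains is narrower. Appendix A item 1d allows for no MSOT image. The accrual allowance in 10.3.1 is for dropouts on the way to the enrollment target, not for missing volumes among those scanned. Missing values are not imputed. So 50 and 45 are ceilings on the pair count, and no expected count is stated.

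**Conclusion.** The two paired-t power statements in Protocol 10.2 are wrong as worded. The values 0.4 and 0.43 SD are approximately the smallest differences with 80% power (exactly 0.404 and 0.427 SD). Below them power drops quickly, to 55% at 0.3 SD and 28% at 0.2 SD with 50 pairs. This rests only on the plan's own inputs and the standard noncentral t calculation.

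Two stronger readings should be resisted. The power calculation itself is not in error: the figures at exactly 0.4 and 0.43 SD are right. Nor do the documents show that fewer than 50 or 45 volume pairs will be obtained, only that the full number is not ensured. The rows for 40, 30 and 20 pairs are illustrations under assumed counts, not predictions.

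**What to change.** In Protocol 10.2, replace *or less* with *or larger* in both paired-t sentences (0.4 SD at 50 patients, 0.43 SD at 45), to match the correlation and variance-ratio statements beside them.

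Optionally, in the same section, say that 50 and 45 are the maximum numbers of paired tumor volumes, give the number expected, and restate all three quantities (detectable difference, correlation and variance ratio) for that number. If no expected number can be given, a short table by pair count, labeled as an assumed range, would do.

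This is a text change. It needs no added enrollment and alters no test. The only downside is that the stated sensitivity for a secondary outcome looks less favorable.

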3.0 Objectives

This IDE FDA approved study will involve the interaction with patients that are scheduled for routine standard of care surgery. It will be a single-arm study that is designed to provide safety information regarding the use of the Acuity MSOT device in the clinical setting and the ability of MSOT imaging data to correlate with clinical findings identified via pathology. We will initially study the safety data in 10 patients, and will expand the study with FDA approval to include 40 more patients after an interim analysis (refer to section 10.3 for more details).

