4.0 Patient Selection

4.1 Inclusion Criteria

- 4.1.1 Patients with an identified solid tumor, i.e. breast (Stage I-IV), melanoma (Stage I-IV), HNSCC (Stage I-III), pancreatic (Stage I-III), ovarian (Stage I-IV) that is scheduled for surgical removal of the tumor and completed standard imaging prior to surgery
- 4.1.2 Have acceptable hematologic status [total hemoglobin (tHb) \geq 10 mg/dL]
- 4.1.3 Patients \geq 18 yrs of age
- 4.1.4 Patient provided a signed and dated informed consent
- 4.1.5 Willing to comply with study procedures and be available for the duration of the study
- 4.1.6 Ability to understand and the willingness to sign an IRB-approved informed consent document.

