10.3 Power and Sample Size

10.3.1 We will initially accrue 10 patients for safety analysis regarding the use of the MSOT device pre- and post-surgery. If there are no grade III-V AEs observed in the patients as defined in CTCAE v5.0 per [Section 8.2](#), we will submit an IDE supplement to request an enrollment expansion for an additional 40 patients, for a total of 50 patients. Up to an additional 55 patients will be accrued (to account for patient dropouts) to enroll 40 patients. Thus, a total of 50 patients will be enrolled and scanned (10 patients in the initial analysis and 40 patients following the interim analysis) in order to gather sufficient data to evaluate the proportion of patients with adverse events that may be associated with the MSOT approach. The MSOT approach is not expected to be related to any adverse events except for a possible slight, reversible reddening and temperature increase of sensitive skin. Nevertheless, this study will allow us to estimate the proportion of unexpected adverse events of grade 3 or higher that are possibly, probably, or definitely related to the MSOT approach. With 50 patients, the upper bound of a 95% Clopper-Pearson exact confidence interval will be less than 20% if the observed rate of adverse events is 8% or less (4 out of 50 or less). We expect that the actual value will be 0 out of 50 – and if this is observed the upper bound of this confidence interval will be 7.1% which would provide a useful upper bound for the potential of adverse events.

The study will be terminated early, after 45 patients in total are enrolled and scanned, if 3 or fewer AEs are observed in the patients scanned by the MSOT device, based on the assumption that the upper limit of the 95% Clopper-Pearson exact confidence interval will be less than 20%. The upper limit of the 95% Clopper-Pearson exact confidence interval will be 7.9%, 11.7%, 15.1% or 18.3% respectively for 0, 1, 2, or 3 observed AEs.

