- ix. Patients with Stage IV pancreatic cancer, Stage IV HNSCC are not surgical candidates and therefore excluded from this study

5. Analysis Populations

- **Safety population:** All subjects who received MSOT readings will be included in the overall safety analysis, with toxicities graded according to NCI CTCAE v5.0. This is primarily a safety analysis study.

6. Summary of Study Population

a. Patient Disposition

- i. Descriptive statistics on the demographics and presenting features will be calculated. Proportions will be calculated for categorical variables and medians with the minimum and maximum will be calculated for continuous variables.

7. Safety Analyses

a. Adverse Events

- i. The severity of the AE will be graded by the Investigator using the NCI CTCAE, version 5.0.
- ii. The adverse events will be estimated by grade, type and relatedness. The first analysis will pool all grade 3 unexpected events that are possibly, probably or

definitely related to MSOT together and then construct a 95% exact Clopper-Pearson binomial confidence interval for this estimate.

b. Temperature Analysis

- i. Measurement of skin temperature will be evaluated where skin temperature greater than 44°C will be recorded and a 95% exact Clopper-Pearson binomial confidence interval constructed.

c. Secondary Analysis

- i. Tumor positivity from pathology reports and MSOT readings will be compared and Pearson correlation coefficient created.
- ii. Deoxy- and oxy-genation levels will be compared to non-tumor values from the same patient. Paired t-tests will be used to compare the values and a Wilcoxon Signed Rank test performed. Median and interquartile range will be reported.

8. Handling of Missing Data

Every effort will be made to collect information at all defined visits including at early withdrawal or dropout. Reasons for missing data will be summarized. However, there will be no imputation of missing data.

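### For tumor targets the pathology reference is nearly always positive, so the agreement-based accuracy in Protocol 10.2 cannot tell an informative reader from one who always calls positive

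*Protocol*

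**What the plan says.** - **Who enters.** Protocol 4.1.1 takes "Patients with an identified solid tumor" from five named cancer types, with the tumor "scheduled for surgical removal of the tumor and completed standard imaging prior to surgery". There is no tumor-free or benign-lesion group. Protocol 3.0: "It will be a single-arm study that is designed to provide safety information regarding the use of the Acuity MSOT device".
- **How many.** Protocol 10.3 plans that "a total of 50 patients will be enrolled and scanned", and allows the study to end at 45.
- **Reference and measure.** Protocol 10.2 compares MSOT with pathology after resection. For binary outcomes it gives an exact Clopper-Pearson interval and says: "Accuracy is defined as the number of patients where the MSOT and standard of care approach are in agreement". It adds that other characteristics can be examined, "including sensitivity, specificity, positive predictive value and negative predictive values". These carry no target precision and no minimum number of negatives.
- **What is imaged.** The target may be a tumor or a lymph node (Protocol 3.2.1). Appendix A records which (item 1a), whether neoadjuvant therapy was given (1c), and whether pathology found tumor (3b).
- **SAP.** Section 7.c.i summarizes pathology against MSOT positivity with a Pearson correlation and does not mention accuracy, sensitivity or specificity. Section 7.c.ii says: "Deoxy- and oxy-genation levels will be compared to non-tumor values from the same patient".

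Neither document states the expected share of pathology-positive targets, the tumor/node mix, the node-positive rate or the cut-off for an MSOT-positive call. Neither says whether the person reading the MSOT images is kept unaware of where the tumor lies.

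**The concern.** A patient whose tumor has already been identified and is about to be removed will almost always have a positive specimen. For tumor targets the reference is therefore close to a constant. Agreement with a constant rewards giving the same answer every time, so a high accuracy could come from the entry criteria and not from the device.

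Protocol 3.0 lists, besides safety, the ability of MSOT data to correlate with pathology. If the agreement figure cannot separate a useful reading from an uninformative one, it does not serve that aim. The SAP's alternative, a correlation, needs variation in the pathology result, and that variation may be absent.

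**Working it through.** **Inputs from the documents.** n = 50 planned and 45 at early stop (Protocol 10.3); per-patient agreement and 95% Clopper-Pearson limits (Protocol 10.2). The share of pathology-positive targets, π, is not given, so it is assumed and varied.

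**Check of the method on the plan's own figures.** The documents state no figure for accuracy or specificity, but Protocol 10.3 gives Clopper-Pearson limits for adverse events. With 0 of n, the upper limit is 1 − 0.025^(1/n). For n = 50 this is 7.11% (plan: 7.1%). For 4/50 the upper limit is 19.23% (plan: below 20%). For 0 to 3 of 45 the limits are 7.87, 11.77, 15.15 and 18.27% (plan: 7.9, 11.7, 15.1 and 18.3%). The method reproduces the plan apart from rounding.

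**Step 1: what accuracy measures.** Accuracy = π × Se + (1 − π) × Sp, where Se and Sp are sensitivity and specificity. As π approaches 1, this tends to Se. A reader who always calls positive has Se = 1 and Sp = 0, so accuracy = π.

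**Step 2: size for tumor targets.** Assume π between 95% and 100%. At n = 50, 95% is 47.5, taken as 48.

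| Pathology-negative | Always-positive accuracy, n = 50 (95% CI) | n = 45 (95% CI) | Specificity CI if every negative is called correctly |
|---|---|---|---|
| 0 | 100% (92.9–100) | 100% (92.1–100) | undefined |
| 2 | 96.0% (86.3–99.5) | 95.6% (84.9–99.5) | 15.8–100% |
| 5 | 90.0% (78.2–96.7) | 88.9% (75.9–96.3) | 47.8–100% |
| 10 | 80.0% (66.3–90.0) | 77.8% (62.9–88.8) | 69.2–100% |

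When all m negatives are correct, the lower specificity limit is 0.025^(1/m): 0.025^(1/2) = 0.158 and 0.025^(1/5) = 0.478. If each of 50 targets is independently positive with probability 0.98, the chance of no negatives at all is 0.98^50 = 0.364; with probability 0.95 it is 0.95^50 = 0.077.

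**Step 3: ranking of readers.** Assume an informative reader with Se = Sp = 0.85. Accuracy = 0.85π + 0.85(1 − π) = 0.85 at any π. The always-positive reader scores π and so ranks higher whenever π exceeds 0.85. At π = 0.95 the informative reader's negative predictive value is (0.05 × 0.85) / (0.05 × 0.85 + 0.95 × 0.15) = 0.0425 / 0.185 = 23%, a low figure produced mainly by prevalence.

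**Step 4: effect of node targets.** Let L be the share of node targets, q the share of those that are positive, and assume tumor targets are 97% positive. Expected negatives of 50 = 50 × [L(1 − q) + (1 − L) × 0.03].

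| L | q | Expected negatives | Always-positive accuracy |
|---|---|---|---|
| 0 | – | 1.5 | 97.0% |
| 0.2 | 0.4 | 7.2 | 85.6% |
| 0.2 | 0.2 | 9.2 | 81.6% |
| 0.4 | 0.4 | 12.9 | 74.2% |
| 0.4 | 0.2 | 16.9 | 66.2% |

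The same uninformative reader moves from 97% to 66% through case mix alone. Specificity remains loose: at an observed 80%, 8/10 gives 44.4–97.5%, 12/15 gives 51.9–95.7% (half-width 21.9 points) and 16/20 gives 56.3–94.3% (half-width 19.0 points).

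**Step 5: the SAP correlation.** Pearson's r divides by the product of the two standard deviations. If pathology is positive in every patient, its standard deviation is 0 and r is undefined. The same happens if MSOT is positive in every patient.

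**The case against.** The strongest reply is that this is a safety study. The primary outcomes are adverse events and skin temperature (Protocol 6.1), the sample size rests on adverse events (10.3), and no treatment decision uses the images (7.1). Accuracy occupies one secondary paragraph with no threshold attached. All of that stands, and it limits the weight of the point.

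A reader might also infer more than the documents support:

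- **That almost every patient will be pathology-positive.** This is reasonable for tumor targets only. Nodes may be tumor-free, and neoadjuvant therapy can leave a specimen without tumor. The documents do not give these shares; under the assumptions in Step 4 there could be about 7 to 17 negatives.
- **That specificity and negative predictive value cannot be estimated.** Specificity is undefined only with no negatives, and negative predictive value only with no negative calls. Otherwise they are computable, but imprecise or dominated by prevalence. Protocol 10.2 treats them as optional.
- **That hemoglobin, being present in all perfused tissue, would make any tissue read positive.** Protocol 2.1 says oxygenation state can distinguish tumor from its surroundings. The missing cut-off is a gap, but it does not show that such misreading will occur.
- **That the plan has no check on discrimination.** The site is re-imaged after closure (Table 2, step 28), and SAP 7.c.ii compares hemoglobin values within the patient. These help. However, no pathology is matched to the closed site, and SAP 7.c.ii compares continuous levels, not positive and negative calls.

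Protocol 10.2 does not expressly order pooling over target types. It defines one per-patient count and does not call for a split, so pooling is the natural reading, although Appendix A would allow a split. Finally, sensitivity alone would not expose an always-positive reader either, so a remedy must pair it with a false-positive measure.

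**Conclusion.** The point holds for tumor targets. Entry criteria and reference standard together make agreement nearly identical to sensitivity. On the assumption that 95–100% of targets are positive, a reader with no information would report 96–100%. Specificity from such targets would be undefined or would have an interval spanning half the scale or more.

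If nodes form a material share, pooled accuracy becomes a function of a mix that the plan does not state. In neither case does the figure show what MSOT adds. The SAP correlation does not repair this and may not exist. The arithmetic is exact; the prevalence, node share and node-positive rate are assumptions. The consequence falls on a secondary result and leaves the safety conclusions untouched. It is still worth correcting because the correction is cheap.

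**What to change.** Amend Protocol 10.2 and SAP 7.c together:

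1. Do not use pooled accuracy or the Pearson correlation as the summary for positivity. Report separately by target type, using Appendix A item 1a.
2. For node targets, report sensitivity and specificity against nodal pathology, each with an exact CI.
3. For tumor targets on the pre-surgery scan, report sensitivity with its exact CI beside the false-positive rate in a non-tumor region of the same patient. Read both regions with the same pre-specified positivity rule, with the reader not told which is tumor where feasible, and analyze them as paired within-patient data.
4. Report pathology-negative tumor specimens as counts; do not drop them.

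SAP 7.c.ii already calls for same-patient non-tumor values but does not say which image they come from. Take them from the stored pre-surgery images where these include non-tumor tissue, and add a field to Appendix B, which has none.

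**Cost.** Wording in two documents, one form field and one more region read per image. The separate figures will look less flattering, the node subset will have wide intervals, and the non-tumor regions are presumed negative without confirmation by pathology, which the report should say.
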